After six months; there was a statistically significant difference between mean bone height measurements in the three groups. Pair-wise comparisons between groups revealed that Osteotome showed the statistically significantly highest mean bone height measurement. There was no statistically significant difference between Densah and Piezo; both showed the statistically significantly lowest mean bone height measurements.

Table 4 : Descriptive statistics and results of two-way repeated measures ANOVA test for comparison between bone height measurements (mm) in the three groups

Time	Densah (n = 7)		Piezo (n = 7)		Osteotome (n = 7)		P-value	Effect size (Partial Eta squared)
	Mean	SD	Mean	SD	Mean	SD		
Base line	4.66	0.37	4.7	0.45	4.68	0.26	0.982	0.002
6 months	10.47 ^B	0.59	10.41 ^B	0.49	11.61 ^A	0.53	0.001*	0.550

*: Significant at $P \leq 0.05$, Different superscripts in the same row are statistically significantly different

b. Changes within each group

In all groups; there was a statistically significant increase in bone height after six months.

Table 5 : Descriptive statistics and results of two-way repeated measures ANOVA test for comparison between bone height measurements (mm) at different time periods within each group

Time	Densah (n = 7)		Piezo (n = 7)		Osteotome (n = 7)	
	Mean	SD	Mean	SD	Mean	SD
Base line	4.66	0.37	4.7	0.45	4.68	0.26
6 months	10.47	0.59	10.41	0.49	11.61	0.53
P -value	<0.001*		<0.001*		<0.001*	
Effect size (Partial Eta squared)	0.984		0.983		0.988	

*: Significant at $P \leq 0.05$

[figure not shown]

Figure 2 : Bar chart representing mean and standard deviation values for bone height measurements in the three groups

c. Comparison between amounts of bone gain in the three groups

After six months; there was a statistically significant difference between mean amounts of bone gain in the three groups. Pair-wise comparisons between groups revealed that Osteotome showed the statistically significantly highest mean bone gain. There was no statistically significant difference between Densah and Piezo; both showed the statistically significantly

lowest mean bone gain measurements.

Table 6 : Descriptive statistics and results of one-way ANOVA test for comparison between bone gain (mm) in the three groups

Densah (n = 7)		Piezo (n = 7)		Osteotome (n = 7)		P-value	Effect size (Eta squared)
Mean	SD	Mean	SD	Mean	SD		
5.81 ^B	0.51	5.72 ^B	0.44	6.93 ^A	0.45	<0.001*	0.617

*: Significant at $P \leq 0.05$

[figure not shown]

Figure 3 : Bar chart representing mean and standard deviation values for bone gain in the three groups

IV. Bone width (mm)

a. Comparison between bone width measurements in the three groups

At base line as well as after six months; there was no statistically significant difference between mean bone width measurements in the three groups.

Table 7 : Descriptive statistics and results of two-way repeated measures ANOVA test for comparison between bone width measurements (mm) in the three groups

Time	Densah (n = 7)		Piezo (n = 7)		Osteotome (n = 7)		P-value	Effect size (Partial Eta squared)
	Mean	SD	Mean	SD	Mean	SD		
Base line	7.28	1.53	7.27	1.25	7.36	1.26	0.990	0.001
6 months	7.36	1.73	7.22	1.17	7.12	1.02	0.946	0.006

*: Significant at $P \leq 0.05$

b. Changes within each group

In all groups; there was no statistically significant change in bone width after six months.

Table 8 : Descriptive statistics and results of two-way repeated measures ANOVA test for comparison between bone width measurements (mm) at different time periods within each group

Time	Densah (n = 7)		Piezo (n = 7)		Osteotome (n = 7)	
	Mean	SD	Mean	SD	Mean	SD
Base line	7.28	1.53	7.27	1.25	7.36	1.26
6 months	7.36	1.73	7.22	1.17	7.12	1.02
P-value	0.556		0.736		0.090	
Effect size (Partial Eta squared)	0.020		0.006		0.151	

*: Significant at $P \leq 0.05$

[figure not shown]

Figure 4 : Bar chart representing mean and standard deviation values for bone width measurements in the three groups

c. Comparison between changes in bone width in the three groups

After six months; there was no statistically significant difference between bone width changes in the three groups.

Table 9 : Descriptive statistics and results of Kruskal-Wallis test for comparison between changes in bone width (mm) in the three groups

Densah (n = 7)		Piezo (n = 7)		Osteotome (n = 7)		P-value	Effect size (Eta squared)
Median	Range	Median	Range	Median	Range		
0.2	-0.44 – 0.48	-0.03	-0.5 – 0.33	-0.2	-0.8 – 0.22	0.289	0.139

*: Significant at $P \leq 0.05$

[figure not shown]

Figure 5 : Box plot representing median and range values for changes in bone width in the three groups

V. Crestal bone loss (mm)

At the buccal as well as palatal sides; there was no statistically significant difference between crestal bone loss in the three groups.

Similarly for the overall crestal bone loss (Mean of the buccal and palatal sides), there was no statistically significant difference between crestal bone loss in the three groups.

Table 10 : Descriptive statistics and results of Kruskal-Wallis test for comparison between crestal bone loss (mm) in the three groups

Side	Densah (n = 7)		Piezo (n = 7)		Osteotome (n = 7)		P-value	Effect size (Eta squared)
	Median	Range	Median	Range	Median	Range		
Buccal	0.24	0 – 0.96	0.7	0.45 – 1.2	0.6	0 – 1.14	0.193	0.188
Palatal	0.08	0 – 0.64	0.66	0.3 – 0.9	0.4	0 – 0.82	0.071	0.259
Overall	0.2	0 – 0.73	0.66	0.4 – 1.05	0.43	0 – 0.97	0.073	0.263

*: Significant at $P \leq 0.05$

[figure not shown]

Figure 6 : Box plot representing median and range values for crestal bone loss in the three groups

VI. Bone density (HU)

a. Comparison between bone density measurements in the three groups

At base line as well as after six months; there was no statistically significant difference between bone density measurements in the three groups.

Table 11 : Descriptive statistics and results of Kruskal-Wallis test for comparison between bone density measurements (HU) in the three groups

Time	Densah (n = 7)		Piezo (n = 7)		Osteotome (n = 7)		P-value	Effect size (Eta squared)
	Median	Range	Median	Range	Median	Range		
Base line	266.4	106.6-464.4	224.8	124.9-412.1	248.8	166.2-523.9	0.754	0.023
6 months	660.3	350.9-740.2	560.4	388.1-701	530.4	444.8-890.7	0.580	0.031

*: Significant at $P \leq 0.05$

b. Changes within each group

In all groups; there was a statistically significant increase in bone density after six months.

Table 12 : Descriptive statistics and results of Wilcoxon signed-rank test for comparison between bone density measurements (HU) at different time periods within each group

Time	Densah (n = 7)		Piezo (n = 7)		Osteotome (n = 7)	
	Median	Range	Median	Range	Median	Range
Base line	266.4	106.6-464.4	224.8	124.9-412.1	248.8	166.2-523.9
6 months	660.3	350.9-740.2	560.4	388.1-701	530.4	444.8-890.7
P-value	0.018*		0.018*		0.018*	
Effect size (d)	3.996		3.996		3.996	

*: Significant at $P \leq 0.05$

[figure not shown]

Figure 7 : Box plot representing median and range values for bone density measurements in the three groups (Circles represent outliers)

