### **Objective**

Evaluation of implant primary and secondary stability, bone gain and density using different techniques (Osteotome technique, Densah drills technique, Piezosurgery) in crestal sinus lifting.

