### Pre-surgical Therapy:

Before the surgery, each patient will be given careful instructions in proper oral hygiene measures. A full mouth supragingival and subgingival scaling and root planning procedure will be performed under local anesthesia using ultrasonic as well as hand instrumentation.

-Cone-beam computed tomography (CBCT) will be taken to estimate the height and width of the bone crest and bone density.

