Statistical Analysis

Numerical data were explored for normality by checking the distribution of data and using tests of normality (Kolmogorov-Smirnov and Shapiro-Wilk tests). All data showed normal (parametric) distribution except for changes in bone width, crestal bone loss as well as bone density data which showed non-normal (non-parametric) distribution. Parametric data were presented as mean, standard deviation (SD) values while non-parametric data were presented as median and range values. For parametric data; two-way repeated measures ANOVA test was used to compare between the groups as well as to study the changes by time within each group. One-way ANOVA test was used to compare between mean age values in the three groups. Bonferroni's post-hoc test was used for pair-wise comparisons when ANOVA test is significant. For non-parametric data; Kruskal-Wallis test was used to compare between the three groups. Wilcoxon signed-rank test was used to compare between bone density values at base line and after six months. Gender data were presented as frequencies and percentages. Fisher's Exact test was used to compare between the three groups. The significance level was set at $P \leq 0.05$. Statistical analysis was performed with IBM SPSS Statistics for Windows, Version 23.0. Armonk, NY: IBM Corp.

Results

I. Demographic data

There was no statistically significant difference between gender distributions in the three groups. There was also no statistically significant difference between mean age values in the three groups.

Table 1: Descriptive statistics and results of Fisher's Exact test and one-way ANOVA tests for comparisons between demographic data of the three groups

Demographic data	Densah (n = 7)	Piezo (n = 7)	Osteotome (n = 7)	P-value
Gender [n, (%)]				
Male	2 (28.6%)	3 (42.9%)	4 (57.1%)	0.854
Female	5 (71.4%)	4 (57.1%)	3 (42.9%)	
Age [Mean, SD]	50.7 (5.6)	49.3 (7.2)	50.1 (7.7)	0.927

*: *Significant at $P \leq 0.05$*

II. Implant stability (RFA)

a. Comparison between groups

At base line; there was a statistically significant difference between mean implant stability measurements in the three groups. Pair-wise comparisons between groups revealed that Densah showed the statistically significantly highest mean implant stability. Osteotome showed statistically significantly lower mean value. Piezo showed the statistically significantly lowest mean implant stability.

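### Bone density: techniques are compared only on raw HU, so no baseline-adjusted comparison or between-technique comparison of gain is reported

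*SAP*

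**What the plan says.** The protocol's Objective section names density among the outcomes: "Evaluation of implant primary and secondary stability, bone gain and density using different techniques". Under Pre-surgical Therapy, CBCT "will be taken to estimate the height and width of the bone crest and bone density", and the Evaluation section repeats the density measurement at six months, at loading.

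For data judged non-normal, a class that includes density, the SAP's Statistical Analysis section uses Kruskal-Wallis between groups. For change in density it says "Wilcoxon signed-rank test was used to compare between bone density values at base line and after six months".

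Results section VI then gives two analyses:

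- **Table 11, between groups:** raw HU at each time separately, p = 0.754 at baseline and p = 0.580 at six months. The conclusion is "At base line as well as after six months; there was no statistically significant difference between bone density measurements in the three groups".
- **Table 12, within groups:** "Descriptive statistics and results of Wilcoxon signed-rank test for comparison between bone density measurements (HU) at different time periods within each group", with p = 0.018 and d = 3.996 in all three groups.

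The section stops there. Height and width each have a further subsection comparing change between groups: Table 6, "Descriptive statistics and results of one-way ANOVA test for comparison between bone gain (mm) in the three groups", and Table 9, "Descriptive statistics and results of Kruskal-Wallis test for comparison between changes in bone width (mm) in the three groups".

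**The concern.** The study asks how three techniques compare on density, but the patient's own preoperative reading is never used when the techniques are compared. The reader gets one unadjusted null test with seven patients per group and no between-technique HU difference with a confidence interval.

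Non-normality does not explain the gap. Change in width was also classed as non-normal, and Table 9 still compares it between groups.

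Table 12 may look as if it fills the gap, since three identical effect sizes suggest equal gains. If that statistic depends only on group size and direction of change, it supports no such reading.

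**Working it through.** **1. Reproducing Table 12.** Inputs: n = 7 per group; assume all seven differences are positive.

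- Rank sum: W = 7 × 8/2 = 28. Its null mean is 14 and its null variance is 7 × 8 × 15/24 = 35.
- z = (28 − 14)/√35 = 2.366, so the two-sided asymptotic p = 0.018, as printed (the exact value is 2/128 = 0.0156).
- One decrease of the smallest rank would give p = 0.028, so p = 0.018 means that every patient rose.
- With z/√7 as the effect-size correlation, d = 2z/√(7 − z²) = 2 × 2.366/√(7 − 5.598) = 3.996, as printed (4.000 with z unrounded).

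Both figures are therefore fixed once all seven patients rise, whatever the amount. The medians nevertheless rose by different amounts:

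| Technique | Baseline median | Six-month median | Difference of medians |
|---|---|---|---|
| Densah | 266.4 | 660.3 | +393.9 |
| Piezo | 224.8 | 560.4 | +335.6 |
| Osteotome | 248.8 | 530.4 | +281.6 |

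These are differences of medians, not medians of paired gains, which the SAP does not give.

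**2. Effect of adjustment on precision.** The within-group correlation r is not reported, so a range is assumed. ANCOVA multiplies the error variance by 1 − r². Estimating the slope multiplies the expected variance of a pairwise difference by 1 + 1/(21 − 3 − 2) = 1 + 1/16. The Bonferroni t for three comparisons goes from 2.639 (18 df) to 2.655 (17 df). The approximate ratio of interval widths is √[(1 − r²)(17/16)] × 2.655/2.639.

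| r | 1 − r² | (1 − r²)(17/16) | Width ratio |
|---|---|---|---|
| 0 | 1.00 | 1.063 | 1.037 |
| 0.3 | 0.91 | 0.967 | 0.989 |
| 0.5 | 0.75 | 0.797 | 0.898 |
| 0.7 | 0.51 | 0.542 | 0.741 |

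Break-even is at r of about 0.26.

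For a rough HU scale, take SD = range/2.704 (a normal-theory value for n = 7). The pooled six-month SD is then about 143 HU. The unadjusted Bonferroni half-width is 2.639 × 143 × √(2/7), about 202 HU. Multiplied by the ratios above, it becomes about 209, 199, 181 and 149 HU. The largest difference between six-month medians is 660.3 − 530.4 = 129.9 HU.

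**3. Power.** Simulation with 40,000 trials per r, bivariate normal data, seven per group, equally spaced means, and Cohen f = 0.738 (80% power for one-way ANOVA):

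| r | Kruskal-Wallis, raw six-month | Quade rank ANCOVA | Kruskal-Wallis, change |
|---|---|---|---|
| 0 | 0.757 | 0.753 | 0.445 |
| 0.3 | 0.756 | 0.788 | 0.604 |
| 0.5 | 0.755 | 0.844 | 0.756 |
| 0.7 | 0.756 | 0.935 | 0.935 |

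Under the null, Kruskal-Wallis rejects at 0.043–0.045 and Quade at 0.050–0.053. The change column assumes equal variances at the two times. Copying Table 9 for density would lose power if r were below about 0.5.

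**4. Would the result change?** p = 0.580 corresponds to F(2,18) = 0.56. Holding the group differences fixed and dividing F by 1 − r², on 2 and 17 df, gives p of about 0.55, 0.49 and 0.36 at r = 0.3, 0.5 and 0.7. Reaching 0.05 would need r of about 0.92.

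**The case against.** The strongest opposing case has five parts.

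- **Wording.** The protocol attaches gain to vertical bone and lists density separately, so Table 11 can be said to answer it literally. Patients are randomised, so the six-month difference and the difference in gain have the same expectation. This stands, and it is why no bias is claimed. It does not excuse leaving out the baseline reading or a HU difference with an interval.
- **Low correlation is plausible.** Every patient receives xenograft, and mean height goes from about 4.7 mm to 10.4–11.6 mm (Table 4), so more than half the six-month height is new. The documents do not define the region in which HU is read. If it includes graft, r could be low and the gain negligible. This stands, and it is why r should be reported.
- **The power illustration uses a large effect.** Table 11 implies f of about 0.18 (from eta squared 0.031) or 0.25 (from p = 0.580). At those values raw Kruskal-Wallis has power of about 0.09 and 0.13. Quade at r = 0.7 has about 0.13 and 0.20. Power is poor either way. The simulation also assumes normality, whereas the SAP calls density non-normal.
- **Density is not unique.** Implant stability also has no reported between-group comparison of change (Tables 2–3), and no outcome in the SAP has confidence intervals. Both are true, but neither supplies the missing density comparison.
- **An estimate is printed.** Table 11 gives a between-group eta squared of 0.031 at six months. That is an overall figure; it says nothing about which techniques differ, or by how many HU.

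**Conclusion.** The concern holds. Table 11 is valid and unbiased under randomisation, and the baseline medians are similar (p = 0.754). It is, however, an incomplete answer to a stated objective, and Table 12's effect size carries no information about the size of the gain.

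The benefit of adjustment depends on the unreported r: from a 4% loss in interval width at r = 0 to a 26% narrowing at r = 0.7. The percentages assume a linear baseline relation with a common slope and variance across groups; the HU half-widths also rest on SDs guessed from ranges. The null finding would probably survive. What would change is that the reader could see which HU differences the data leave open. The point is worth acting on because it is cheap, but it does not invalidate a reported test.

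**What to change.** Keep Table 11 as reported and add the following, labelled post hoc and supplementary:

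1. **Test:** Quade rank ANCOVA. Regress ranked six-month HU on ranked preoperative HU and compare the residuals across the three groups (error df 18).
2. **Estimates:** baseline-adjusted pairwise HU differences with Bonferroni-adjusted confidence intervals, from an ordinary or robust ANCOVA (error df 17).
3. **Correlation:** the pooled within-group correlation between preoperative and six-month HU, so that the gain from adjustment can be judged.
4. **Table 12:** each group's median paired HU gain beside d, with a note that 3.996 follows from n = 7 with all patients rising.

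Prefer items 1 and 2 to a Kruskal-Wallis test on change modelled on Table 9. The cost is a short re-analysis of data already held and one error degree of freedom for the ANCOVA estimates. If r proves near zero, the adjusted intervals would be about 4% wider than unadjusted ones.
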